**Effect of EPA and HMB on Strength in ICU Patients**

**NCT01270516**

**3-12-21**

**Research Description**

## **Form B: Research Description**

### **1. Background.**

Over the past 20 years there has been a dramatic growth in the numbers of patients requiring mechanical ventilation to sustain life in the United States. At most large medical centers, the number of patients needing more than transient mechanical ventilation for respiratory insufficiency has approximately tripled over the past 10 years. To deal with this burgeoning number of mechanically ventilated patients, stand-alone ventilator units have been created in the United States in most large cities, with literally hundreds of mechanically ventilated patients placed in such units in each of the large metropolitan areas in this country. In aggregate, we estimate that as many as 50,000 patients are on sustained mechanical ventilation at any given time in the United States. The total cost of caring for these patients now consumes approximately 6% of the yearly health care budget, or upwards of 1% of the United States GNP.

We have recently completed a study at the University of Kentucky that indicates that a major process contributing to respiratory failure in critically ill patients is respiratory muscle weakness. This work found that the average patient in the UK ICU has a diaphragm pressure generation (PDI) in response to phrenic magnetic twitch stimulation of only  $8 \pm 3$  cm H2O, compared to an accepted normal value of 30 cm H2O for healthy adults. Moreover, we found that 70% of patients have twitch PDI measurements that are less than a third of normal. These data suggest, moreover, that severe respiratory muscle weakness contributes to respiratory failure in mechanically ventilated patients, with the weakest patients taking the longest to wean from mechanical ventilation and having the highest mortality.

Unfortunately, there is currently no specific defined treatment to prevent or reverse respiratory muscle weakness in mechanically ventilated patients. Theoretically such a treatment may improve outcomes in these patients, reducing the time required to wean from mechanical ventilation, shortening hospital duration, and potentially improving mortality. While no specific treatment is available for patients with respiratory muscle weakness, animal studies indicate that there are defined cellular pathways (calpain, caspase, free radicals, the proteasomal pathway) that contribute to diaphragm weakness in response to the clinical stresses placed on critically ill patients (i.e. inactivity due to mechanical ventilation, inflammation secondary to infection, hyperglycemia). Moreover, these pathways can be blocked and diaphragm dysfunction prevented in these animal models of disease by administration of either eicosapentaenoic acid (EPA, a caspase and calpain inhibitor) or hydroxymethylbutyrate HMB (a caspase and PKR inhibitor). Both these agents, EPA and HMB, have been safely administered to many patients in previous studies (EPA to prevent vascular disease, HMB to improve muscle function in cancer patients). Neither drug has been reported to cause significant side effects at the dosages chosen. Both are over the counter supplements that can be obtained without prescription in drug stores, health food stores and over the internet.

Based on this information, we postulated that it may be possible to prevent the development of diaphragm and limb muscle weakness in critically ill, mechanically

ventilated patients by early administration of either EPA or HMB. We recently completed an IRB approved pilot study examining the effects of EPA and HMB on diaphragm strength in a small group of mechanically ventilated MICU patients. This study found that both agents induced increases in diaphragm strength and that administration of HMB reduced the duration required to wean patients from mechanical ventilation. These pilot data were used to submit a grant application to the NIH, entitled “**Treatment of Skeletal Muscle Dysfunction in ICU Patients**”, which was subsequently funded.

## 2. Objectives.

The objective for this study is to determine if administration of either EPA or HMB can prevent or reverse the development of respiratory muscle weakness in critically ill, mechanically ventilated patients. We plan to randomize patients accepted into this protocol to administration of either a control (saline enteral control solution), EPA administration, HMB, or the combination of EPA +HMB. Drugs will be administered for 10 days and measurements of muscle strength (diaphragm and quadriceps), muscle size (diaphragm and quadriceps thickness by ultrasound), and muscle signaling protein profile (obtained using vastus lateralis muscle biopsy specimens) will be performed immediately before and immediately after the period of drug administration (days 1 and 11). An additional assessment of muscle strength, muscle size and signaling protein profile will be made at 10 days after completion of the drug administration regimen (i.e. on day 21). As part of the study, patients will be weaned from mechanical ventilation using the University of Kentucky ventilator separation protocol, the nutritional regimen will be reviewed with the MICU nutritionists to ensure it conforms to study requirements, and it is expected that patients will receive standard MICU mobilization therapy by physical therapy.

We will also perform a chart review and assess ventilator mechanics (respiratory system static compliance and inspiratory airway resistance) at the time of strength assessment. We would expect that mean diaphragm and quadriceps muscle strength and size measurements will be similar for four groups immediately before initiation of drug administration. Our hypothesis will be supported if post drug administration diaphragm and limb muscle strength are higher for patients receiving EPA , HMB and/or the combination of EPA+HMB when compared the control group receiving no active drug. We will also determine if administration of these agents shortens the time required to wean patients from mechanical ventilation.

## 3. Study Design.

The basic study design is to:

(a) measure magnetic stimulated diaphragm Pdi twitch and quadriceps twitch strength, measure diaphragm and quadriceps thickness using ultrasonography, obtain a vastus lateralis muscle biopsy, determine lung mechanics (respiratory system compliance, determine airway resistance), and perform a chart review,

(b) randomize patients to treatment with either:

Placebo this will be given as two tablespoons of salt water solution, 1.5 grams of amino acids and 0.2 teaspoons of corn oil every 12 hours,

Eicosapentaenoic acid (EPA); this will be given as two tablespoons of salt water, 1.5 grams of amino acids and 1000 mg EPA every 12 hours,

Hydroxymethylbutyrate (HMB); this will be given as two tablespoons of salt water solution, 1500 mg HMB and 0.4 teaspoons of corn oil every 12 hours,

HMB and EPA; two tablespoons of salt water, 1500 mg HMB and 1000 mg EPA every 12 hours.

(c) continue drugs for 10 days then

(d) on day 11, remeasure magnetic stimulated diaphragm Pdi twitch and quadriceps twitch strength, measure diaphragm and quadriceps thickness using ultrasonography, obtain a vastus lateralis muscle biopsy, and determine lung mechanics (respiratory system compliance, determine airway resistance), and

(e) on day 21, remeasure magnetic stimulated diaphragm Pdi twitch and quadriceps twitch strength, measure diaphragm and quadriceps thickness using ultrasonography, and determine lung mechanics (respiratory system compliance, determine airway resistance) if the patient is still requiring mechanical ventilation.

In preliminary work we have verified that HMB easily goes into solution when placed in saline. In addition, EPA goes into solution easily when placed in a mixture of oil and saline (in a 1:3 ratio). We will plan to administer the agents at 7 AM and 7 PM whenever possible so that the administration of these agents does not interfere with dosing of patient medications. The IDS will perform both blinding and randomization of the agents provided. The IDS will perform randomization using an online computer program ([www.Randomization.com](http://www.Randomization.com)). Note that HMB has no side effects at any dosage. At higher doses than the doses to be used in the current study, EPA can interfere with clotting and potentiate the effects of aspirin and Coumadin.

For each chart review we will obtain the following information: age, sex, diagnoses, medications, reason for institution of mechanical ventilation, vital signs, bedside parameters of mechanical ventilation use (including mode of ventilation, duration of ventilation, level of oxygen, breath volume and rate, % triggered breaths), most recent arterial blood gas values, chest radiograph readings, recorded assessments of mental status.

#### 4. Study Population.

Adult patients requiring mechanical ventilation for respiratory failure for more than 24 hours in one of the University of Kentucky adult ICU's will be asked to participate. An additional inclusion criterion is that the attending physician caring for the patient must anticipate that the patient is likely to remain on mechanical ventilation for more than 24

hours. We will include patients regardless of gender, race, or adult age. It is hoped that sufficient minorities and women will be studied so that the subject population is representative of the general patient population, but we will be somewhat constrained by the numbers of available patients and the day to day makeup of the patient population in the UK ICU's. Inclusion of minorities and women will make the study results more generally applicable.

Patients will be excluded: (a) if the physician caring for the patient determines that the patient is too unstable to tolerate these measurements, (b) if the patient requires high dose pressors (more than 15 mcg/min of norepinephrine or more than 15 mg/kg/min of dopamine), (c) if the patient requires more than 80% FiO2 or more than 15 cm H2O of PEEP, (d) if the patient has a cardiac pacemaker or implanted defibrillator, (e) if the patient has received neuromuscular blocking agents within the 48 hours preceding testing, (f) if the patient has a history of a preexisting neuromuscular disease, (g) if the patient has a history of recent variceal bleeding, (h) if the patient has profound and uncorrectable hypokalemia (less than 2.5) or hypophosphatemia (less than 1.0), (i) if the patient is a pregnant female, (j) if the patient is a prisoner, (k) if the patient is institutionalized, (l) if the patient is allergic to fish, (m) if the patient cannot receive enteral medications, (n) if it is thought that the patient is terminal and will have care withdrawn within days, (o) in addition, if a given patient has a coagulopathy at the time of enrollment into the study (defined as an elevation of the INR above 1.5, an aPTT 50% or more above the normal range, or a platelet count less than 60,000), we will not perform muscle biopsies on the patient but will collect the other data planned.

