**Ventilator Separation Protocol:** All patients will be weaned using the University of Kentucky Ventilator Separation Protocol. This protocol is currently employed in all University of Kentucky adult intensive care units and provides a standardized approach to weaning patients from mechanical ventilation. Every morning mechanically ventilated patients are evaluated for potential weaning trial employment. Inclusion criteria for a spontaneous breathing trial (SBT) includes evidence that the patient is: (a) awake, (b) has a gag reflex, (c) has a cough reflex, (d) has a RASS scale of -1 to 0, (e) has a FiO2 ≤50% and PEEP applied ≤ 6 H2O, (f) has a pH ≥7.35, (g) has a MAP of ≥ 65 mm Hg, (h) is off pressor drips (e.g. epinephrine) save for doses of dopamine ≤ 5 mcg/kg/min or dobutamine ≤ 5 mcg/kg/min, and (i) is not on an intra-aortic balloon pump. Exclusion criteria include increased intracranial pressure, use of paralytics, active seizures, excessive agitation and active myocardial ischemia. If the patient meets all inclusion criteria and has no exclusion criteria, sedation will be reduced and the patient will receive a spontaneous breathing trial (SBT) for 1 hour, with an ABG drawn at the end of the trial. During the trial patients will be monitored serially for evidence of weaning success or failure (i.e. observed at the 5, 15, 30, 45 and 60 minute time points into the trial). Trials will be stopped if any of the following events occur: (a) oxygen saturation falls below 90% for more than three minutes, (b) the heart rate increases above 130 or falls below 60, (c) systolic blood pressure falls below 90 or increases above 180, (d) the mixed venous oxygen saturation falls below 60 mm Hg (if monitored), (e) the respiratory rate increases above 35 or the RSBI increases above 100, (f) the patient develops chest pain or a new dysrhythmia, (g) the patient's mentation worsens, or (h) the patient develops diaphoresis, distress or excessive anxiety. Blood gases will be examined at the end of trials and trials will be judged a success if, in addition to passing the criteria in the preceding sentence, the final paO2 is greater than 60 mm Hg and there is no respiratory acidosis. If the patient achieves a successful SBT, the attending will be asked for an extubation order. If the trial fails, the patient will be placed on their previous ventilator mode and settings. If trial failure is associated with evidence of excessive sedation, sedation levels will be reduced in preparation for the next day trial.

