#### 10. Safety Precautions.

To minimize the risk of bleeding from balloon placement, patients with variceal bleeds will be excluded from this study. Because assessment of PdiTw involves transient removal from mechanical ventilation, patients requiring high levels of PEEP, high levels of oxygen or in severe shock will be excluded from study. As indicated in above paragraphs, these procedures have been extensively employed in London, UK to evaluate patients in both outpatient and ICU settings and the investigators there have not observed complications with either balloon placement or magnetic stimulation. In fact there are no reported adverse effects using magnetic stimulation to assess peripheral nerves except for an isolated report of interference with pacemaker function in one patient. For this reason, we will also exclude patients with pacemakers from this study. As per standard ICU protocols at UK, during all measurements all patients will be connected to invasive or non-invasive blood pressure transducers, EKG monitors, and pulse oximetry monitors, providing a continuous assessment of patient pulse rate, blood pressure, and oxygen saturation during assessments. If desaturation to less than 90%, a raise in heart rate by more than 20 beats, a rise in mean blood pressure more than 10 torr or a fall in mean blood pressure of more than 10 torr is noted, measurements will stop. The PI will return at 24 hours after each study to the patient's bedside to ascertain if any untoward events have occurred and to elicit feedback regarding any concerns that the patient and/or their family and/or the nursing staff caring for the patient may have. If problems are encountered they will be reported to the IRB and data monitoring board.

To minimize the risk that the patient's privacy would be compromised, all data will be placed into a file at the conclusion of the bedside study and this file will be placed into a locked file cabinet in the office of the PI. Each file will be assigned a research number, and all data abstracted from the file of an individual subject will be referred to in later data analysis by this patient file number with no reference to any identifiable patient characteristics (e.g. name, SS number, hospital number). The mean data for the study will also be placed in a mean data file and this information also kept in the locked file drawer in the PI's office.

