#### 17B. Safety Monitoring

During the execution of this protocol the nurse assigned to the patient will be asked to be present in the room to provide an ongoing assessment of patient vital signs. As per standard ICU protocols at UK, during all measurements all patients will be connected to invasive or non-invasive blood pressure transducers, EKG monitors, and pulse oximetry monitors, providing a continuous assessment of patient pulse rate, blood pressure, and oxygen saturation. If desaturation to less than 90%, a raise in heart rate by more than 20 beats, a rise in mean blood pressure more than 10 torr or a fall in mean blood pressure of more than 10 torr is noted, measurements will stop and the patient will be

returned to mechanical ventilation. As per standard ICU protocols at UK, during all measurements all patients will be connected to invasive or non-invasive blood pressure transducers, EKG monitors, and pulse oximetry monitors, providing a continuous assessment of patient pulse rate, blood pressure, and oxygen saturation during assessments. If desaturation to less than 90%, a raise in heart rate by more than 20 beats, a rise in mean blood pressure more than 10 torr or a fall in mean blood pressure of more than 10 torr is noted, measurements will stop. The PI will return at 24 hours after each study to the patient's bedside to ascertain if any untoward events have occurred and to elicit feedback regarding any concerns that the patient and/or their family and/or the nursing staff caring for the patient may have. If problems are encountered they will be reported to the IRB and data monitoring board. The PI or [name] will also return to inspect the muscle biopsy site daily for seven days to confirm adequate healing at the site.

The PI will provide the nurse with his cell phone number at the completion of each data collection with instructions to call the PI if any untoward events occur within the following 24 hours. In addition, the PI will return at 24 hours after each study to the patient's bedside to ascertain if any untoward events have occurred and to elicit feedback regarding any concerns that the patient and/or their family and/or the nursing staff caring for the patient may have. If problems are encountered they will be reported to both the monitoring board described in the preceding section and to the IRB board by the PI.

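### Exclusion (b) prints the dopamine limit in mg/kg/min, 1,000 times the same number in mcg/kg/min, so its dopamine limb cannot exclude anyone as written

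*Protocol*

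**What the plan says.** Protocol section 4 lists the exclusions. Item (b) covers high-dose pressors and sets two numerical limits: "more than 15 mcg/min of norepinephrine or more than 15 mg/kg/min of dopamine".

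Only one other dopamine dose appears in either document. In section 7, the Ventilator Separation Protocol requires patients to be off pressor drips before a spontaneous breathing trial, "save for doses of dopamine ≤ 5 mcg/kg/min or dobutamine ≤ 5 mcg/kg/min".

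Section 10 gives the reason for the exclusion. The twitch measurement briefly takes the patient off the ventilator, so "patients requiring high levels of PEEP, high levels of oxygen or in severe shock will be excluded from study". No dose is given there. Neither document restates or corrects the dopamine limit.

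**The concern.** The two limits in exclusion (b) sit in one parenthesis but use mass units a thousandfold apart: micrograms for norepinephrine, milligrams for dopamine. The breathing-trial criterion in section 7 gives dopamine in micrograms. The number 15 is not in question. The unit is.

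The clause decides eligibility. Section 5 has candidates identified against the inclusion and exclusion criteria, and section 11 rests its view of long-term safety on strict observance of the exclusions. Section 17A has the monitoring board review protocol violations and the eligibility criteria. Exclusion (b) is also the only place where pressor dose is quantified for eligibility. If its dopamine limit cannot be reached, no dopamine dose can exclude a patient under it or count as a breach of it.

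**Working it through.** The protocol derives nothing here, so there is no calculation of its own to reproduce. The check is a unit conversion and a comparison within the documents.

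**Inputs**
- Dopamine limit as printed: 15 mg/kg/min (Protocol section 4, exclusion (b)).
- Norepinephrine limit in the same clause: 15 mcg/min.
- Dopamine ceiling at a breathing trial: 5 mcg/kg/min (Protocol section 7).
- Body weight: the documents give none, so 50, 70 and 100 kg are assumed.
- 1 mg = 1,000 mcg; 1 day = 1,440 min.

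**Conversion**
- 15 mg/kg/min × 1,000 = 15,000 mcg/kg/min.
- Against the same number in micrograms: 15,000 / 15 = 1,000.
- Against the breathing-trial ceiling: 15,000 / 5 = 3,000. With the unit corrected, the ratio would be 15 / 5 = 3.

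**Dose needed to reach the limit** (limit × weight, then × 60 for an hour or × 1,440 for a day)

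| Assumed weight | As printed, per min | As printed, per hour | As printed, per day | At 15 mcg/kg/min, per day |
|---|---|---|---|---|
| 50 kg | 750 mg | 45 g | 1,080 g | 1.08 g |
| 70 kg | 1,050 mg | 63 g | 1,512 g | 1.512 g |
| 100 kg | 1,500 mg | 90 g | 2,160 g | 2.16 g |

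For example, at 70 kg: 15 × 70 × 1,440 = 1,512,000 mg = 1,512 g a day.

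**Reading the comparison.** The section 7 dose is used only to show which unit the protocol uses for dopamine. A ceiling for attempting a breathing trial and a limit for entering the study serve different purposes and need not agree, so 5 against 15 is not itself an inconsistency.

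**The case against.** The strongest reply is that this is a one-letter slip with no demonstrated consequence. The criterion opens by naming high-dose pressors, so its intent is plain. Screening is done by experienced critical-care physicians, who would not read the limit literally. Other protections do not depend on it: exclusion (a) applies "if the physician caring for the patient determines that the patient is too unstable to tolerate these measurements", section 10 separately keeps out patients in severe shock, and under section 17B, if "a fall in mean blood pressure of more than 10 torr is noted, measurements will stop". All of this stands, and it is why the point is minor. It does not make the printed limit correct, and a reader should not have to guess the threshold.

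Two further points have some force. First, neither document states a maximum dopamine dose, so the claim that the limb cannot exclude anyone is an inference. It is a safe one, since the printed limit means more than a kilogram of drug a day at every weight tried. Second, a micro sign in the source file could have been misread as the letter m. That cannot be ruled out completely, but the protocol spells out mcg in the same parenthesis and again in section 7, so a typing error is much more likely. The source page would settle it.

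It is also true that an erratum cannot change enrolment now that the SAP reports results. It would still correct the public record of who was eligible.

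**Conclusion.** The concern holds. As written, the dopamine limit in exclusion (b) is 1,000 times the same number in mcg/kg/min, and that limb cannot operate. The factor of 1,000 follows from the units alone. Only the illustrative daily doses depend on the assumed weights of 50 to 100 kg. That 15 mcg/kg/min was intended is a presumption for the clinicians to confirm.

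The fault is confined to one limb of one criterion, and the norepinephrine limb still works. The documents do not show that anyone was wrongly enrolled. Sample size, power and the planned analysis are not touched. Severity is minor; confidence that the text is wrong as printed is high.

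**What to change.** 1. Check the source page and have the responsible clinicians confirm the intended dopamine limit.
2. Issue a one-line erratum to exclusion (b), changing mg/kg/min to mcg/kg/min. If 15 is confirmed, nothing else in the clause changes.
3. Check whether any of the patients in the SAP's arm-size table (20 + 17 + 18 + 18 = 73) was above the confirmed limit at entry. The starting point is the chart review in section 3: "For each chart review we will obtain the following information: age, sex, diagnoses, medications". That list names medications but not infusion rates, so where the rate was not captured it must come from the medical record.
4. Report the result, including a count of zero, where the study population is described.

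The erratum costs one line. The check costs one pass through the chart-review data for 73 patients, plus some record look-ups where doses are missing. There is no statistical cost.
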